***Cluster Intervention (67 participants):**

The intervention group will receive at the beginning a motivational interview with a personalized portfolio provided by a nutritionist on the Mediterranean diet and adherence to the diet: with information on the food components; desirable frequency of intake; recipes, use of olive oil, walnuts, hazelnuts and almonds. Individual guidelines will be planned individually to improve the lipid profile and improve food choices considering dietary habits, socioeconomic status and nutritional needs (and the score obtained on the MEDAS scale).

At weeks 4 and 12 (virtual), the patient will have a new interview with the nutritionist to review the recommendations, discuss difficulties with diet adherence, design weekly dietary plans and shopping lists. At week 24 and 48, an in-person visit will be held to perform all the procedures of the baseline visit again (including blood draws).

***Cluster treatment standard (33 participants).**

Baseline visit (in person), In addition to the initial assessment identical to that of the intervention group, general dietary information will be provided in writing, as is currently done in the HIV unit.

New visits will be made at week 24 (in person) and week 48 (in person). The same measurements, dietary assessments and blood draws will be made as at the baseline visit.

Detailing of tasks to carry out for achievement of the goals:

- Task 1. Adherence to the Mediterranean diet, anthropometric and quality of life measurements (objectives 5 and objective 6). All carried out by a trained researcher.
 - Task 1a. 118-item semiquantitative food frequency questionnaire (FFQ), MEDAS questionnaire, and a 24-hour dietary recall .
 - Task 1b. Anthropometric measurements: height and weight will be measured using a mechanical anthropometric scale. BMI (BMI = weight (kg) / [height (cm)]2). Waist circumference halfway between the lower rib margin

and the iliac crest. Hip circumference will be measured as the widest measurement over the buttocks.

- Task 1c. Measuring quality of life using the EQ-5D questionnaire. Specific questions on alcohol consumption patterns and the IPAQ Physical Activity Questionnaire, Simplified Medication Adherence Questionnaire (SMAQ).
- Task 2. Measurement of the profile lipid (for achievement of goals 1 (1a,1b,1c)
 - Task 2a. Blood collection after fasting for more than 8 hours, between 8am and 10am. Serum will be obtained for the usual clinical measurement by means of the practice clinic usual and in the laboratory of Reference from Catalonia for the measurement of total cholesterol, HDL and LDL (according to standard practice). Serum, plasma and cells will be preserved (task 4)
 - Task 2b. With the samples of serum obtained and preserved to -80°C and when recruitment and monitoring have been completed, the analysis of the lipoprotein subclass profile will be performed by means of Proton Nuclear Magnetic Resonance (NMR) in Metabolomics Platform IISPV, CIBERDEM. Rovira i Virgili University, Biofer Teslab. Lipoprotein analysis of serum samples will be performed using Liposcale® (Biosfer Teslab, Reus, Spain), a method based on 2D diffusion-ordered ^1H -NMR spectroscopy. This protocol evaluates lipid concentrations, particle size and number of three different classes of lipoproteins (vLDL), LDL and HDL), as well as the number of particles of nine subclasses (large, medium and small vLDL , LDL and HDL). This technique records 2D ^1H MRN spectra on a BrukerAvance III 600 spectrometer, operating at a proton frequency of 600 MHz to 310 KHz (Bruker (BioSpin , Rheinstetten , Germany). The signal obtained makes it possible to determine the nine lipoprotein subclasses. (J. Clin. Med . 1875.) The study of lipoprotein subclasses makes it possible to obtain a profile that, when compared with a population database, makes it possible to estimate cardiovascular risk based on the lipid composition of the lipoprotein subclasses in a more specific way than by means of the classic scales for estimating cardiovascular risk.
- Task 3. Measurement of arterial stiffness by pulse wave velocity (to achieve objective 3). Arterial pulse wave velocity will be determined by sequential applanation tonometry (Millar Tonometer, SPC-301; Millar Instruments, Houston, TX) in the carotid and femoral arteries synchronized with a three-lead electrocardiogram using the SphygmoCor device (SphygmoCor ; AtCor , Sydney , Australia). Wave arrival latency time will be calculated using a foot-wave method. The surface distance from the suprasternal notch to each recording point will be measured. Total transit distance will be calculated by subtracting the distance between the sternal notch and the carotid from the distance between the sternal notch and the femoral artery. Arterial pulse wave velocity will be calculated using total transit distance divided by time. of latency. HE will reject the measurements of the speed of the wave pulse that do not meet the automatic quality controls specified by SphygmoCor software . Two pulse wave velocity measurements will be averaged for each subject for all calculations.
- Task 4. Study of immunoactivation markers in PBMCs (peripheral blood mononuclear cells) (objective 2a). PBMCs will be obtained from heparinized blood by density gradient centrifugation (Ficoll - Paque ; Amersham Biosciences).

- Task 4a. Flow cytometry. A panel of antibodies will be used to characterize adaptive immune cells, including CD3, CD 45, CD 4, CD8, CCR7, CXCR3, CCR6, CD103, FOXP3, CD25, CD45RA

a

nd

CD45RO. HE will identify the cells T of memory (CD45RA-/CD45RO+) and naïve and effector T cells (CD45RO-/CD45RA+). Within memory cells (CD45RA-), central memory cells (CCR7+) and effector memory cells (CCR7-); and inside of the cells T that are of memory (CD45RO-/CD45RA+), naïve cells (CCR7+) and effector cells (CCR7-). Using lineage marker (CD3+) and cytotoxic lymphocytes (CD8+), helper lymphocytes (CD4+) are separated into subtypes by expression or not of the chemokine receptors type 3 (CXCR3) and 6 (CCR6) such as: Th1 (CXCR3+CCR6-), Th 2 (CXCR3-CCR6-), Th17 (CXCR3-CCR6+) and Th1- Th17 (CXCR3+CCR6+). The percentage of activated cells will be differentiated using the activation markers HLA-DR and CD38. Regulatory T cells will be identified as FOXP3+CD25+. Appropriate positive and negative controls will be performed. Cell populations will be acquired from LSR- Fortessa (UPF central facilities) and analyzed using Flowjo software (Treestar Inc. CA).

- Task 5. Study of inflammatory markers and bacterial translocation (to achieve objective 2b). A multiplex ELISA for different biomarkers: at least the multiplex must include: IL-6, TNF-alpha, IFN-gamma, sCD163, sCD14, MADCAM-1, sCD14 and LPS. Plasma samples will be stored at -80 °C to perform the analysis at the same time in order to reduce variability.
- Task 6. Determination of the levels plasmatic of TMAO (for achievement of aim 4). HE will preserve to -80C all the samples and HE will perform a Once the study is completed, the determination of TMAO levels in fasting plasma will be quantified by stable isotope dilution liquid chromatography with on-line tandem mass spectrometry (LC/MS/MS) on an API 500 triple quadrupole mass spectrometer (AB SCIEX, Framingham, Massachusetts) available at the Bioanalytics department of Middlesex University , London, with whom the PI has a stable collaboration and will allow the measurement to be carried out reliably and consistent.
- Task 7. Upon approval of the amendment (version 1.2 of the protocol), all enrolled patients will undergo a CCTA. CCTAs in the study will be performed in an identical manner to those performed daily in our center as part of routine clinical practice, using identical protocols for both image capture and interpretation/reporting . The radiation dose used will follow the ALARA principle ("as low as reasonably possible"), as low as possible while maintaining image quality. The same principle will apply to the intravenous contrast dose. Patients will sign an updated informed consent to participate in the VIHMET study (insert the name of your study), which will include a specific description of the CCTA, its objectives and associated risks. Once in the study, participants will receive the usual pre-CCTA preparation by specialized nursing staff and directed by cardiologists with experience in cardiac imaging. This includes general recommendations on hydration and fasting, as well as the potential use of a low-dose beta-blocker (or ivabradine) to control heart rate if it is above 70 bpm .
-

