PROTOCOL OF CLINICAL RESEARCH

Randomized Study to Assess the Impact of Mediterranean Diet Optimization on Metabolic Profile, Immune Activation, and Cardiovascular Risk in People with HIV on ART

Version of the protocol and date	Version: 1.2 date: 06/15/2024
Code of the protocol	
Qualification abbreviated either acronym	VIHMET
Promoter	
CRO (when proceed)	If applicable
Research Team	
Principal Investigator [name] HIV Division. Internal Medicine. Hospital del Mar [contact] e-mail: [contact]
 
Researcher(s) contributor(s) [name] Endocrinology Hospital del Mar, Barcelona [contact] e-mail: [contact]
 
[name] HIV Division. Internal Medicine. [contact] E-mail: [contact]
 
[name] Endocrinology Hospital del Mar [contact]

	
E-mail: [name]
 
[name] HIV Division. Internal Medicine. Hospital del Mar [contact] E-mail: [contact]
 
[name] HIV Division. Internal Medicine. Hospital del Mar. [contact] E-mail: [contact]

SUMMARY

Qualification	Randomized Study to Assess the Impact of Mediterranean Diet Optimization on Metabolic Profile, Immune Activation, and Cardiovascular Risk in People with HIV on ART
Goals	
 - Assess changes in metabolic profile and lipid in the week 24 - immunoactivation profile at week 24 - To assess changes in arterial stiffness levels measured by pulse wave velocity at week 24 - Proportion of participants with >20% decrease in TMAO in week 24 compared to baseline. - Proportion of participants with an increase of >2 points in the MEDAS scale of adherence to the Mediterranean diet at week 24 - Proportion of participants improving on the EQ-5D quality of life questionnaire at week 24 - Assess persistence of all changes from Objective 1 to 6 at Week 48 - To evaluate the presence and composition of coronary atherosclerotic plaque by means of coronary CT angiography before and after the intervention.
Design	Rehearsal clinical randomized open

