Inclusion-exclusion criteria	
Criteria of inclusion:
 
 - Participant \geq 18 years. - Infection by HIV confirmed by serology. - Treatment antiretroviral asset (TAR). - Burden viral undetectable during to the less 12 months (HE allows a blip below 200 copies). - LDL >140 mg/ dL . - Mediterranean Diet Adherence Screener (MEDAS) less than 9 points (adherence low) for ease the detection of changes after the intervention. 
Criteria of exclusion:
 
 - Participants in treatment lipid-lowering. - Treatment with anti-inflammatory chronic. - Hepatitis B, C or Others conditions inflammatory chronicles active. - Hypercholesterolemia familiar No treated. - Hypothyroidism No controlled. - Impossibility of give he consent.
Treatments or interventions	Advice dietary, analysis blood, measurement of the pulse arterial
Variables	
Cholesterol total, cLDL, cHDL, triglycerides
 
Number, size and composition of particles of lipoproteins
 
Anthropometric profile
 
CD 3, CD45, CD4, CD8, CCR7, CXCR3, CCR6, CD103, FOXP3, CD25, CD45RA and CD45RO
 
IL-6, TNF-alpha, IFN-gamma, sCD163, sCD14, MADCAM-1, sCD14 and LPS.
 
Rigidity arterial extent by the speed of pulse
 
Trimethylamine -N-Oxide
 
Scale MEDAS of adherence to the diet Mediterranean

	Atheroma plaque (number of plaques) Plaque composition (% fibrosis, % calcium, % fat) Coronary calcium index
--	--

	Questionnaire of quality of life EQ- 5D
Population and No. subjects	100 patients of the unit of HIV
Participating centers	Hospital of the Sea. Barcelona
Study Description	Study comparative of the intervention dietetics conventional with a personalized dietary intervention
Overall duration from the study	January 2025- December 2026
Duration of the study for the patient	48 weeks

Board 1. Calendar of the study / procedures for a subject

	Screening (max 28 days before baseline visit)	visit (randomization)	W4 (+/- 7d)	W12 (+/-7d)	W24 (+/-7d)	W48 (+14-7d)
Type of visit	In person	In person			In person	In person
Intervention group			Virtual	Virtual		
Cluster control			No visit	No visit		
Informed consent	x					
Criteria of inclusion and exclusion	x					
Demographic data	x					
History medical	x					
Related story with HIV	x					
Exam physical		x			x	x
Anthropometric data		x			x	x
Questionnaires (MEDAS, FFQ, SMAQ, EQ- 5D and IPAQ)	x (only MEDAS)	x			x	x
Concomitant medication	x	x		x	x	x

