2. HISTORY OF VERSIONS

Version	Date	Description of the change	Brief justification
1.2	June 15, 2024	Introduction to the amendment Noninvasive coronary artery angiography using CT (CCTA)	Given the possibility of having CCTA experience for coronary plaque detection at our center, this amendment is included to evaluate subclinical coronary disease and possible changes.

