Objective 1. Evaluate changes in the metabolic and lipid profile:

- Objective 1a. To evaluate changes in the lipid profile (total cholesterol, LDL-C, HDL-C, triglycerides) at week 24 compared to baseline.
- Objective 1b To evaluate the number, size and composition of lipoprotein particles by proton magnetic resonance spectroscopy at week 24 compared to baseline.
- Objective 1c. Percentage of people with increased high-density lipoprotein (HDL) levels >5%.
- Objective 1d. To assess changes in the anthropometric profile (weight, body mass index, abdominal circumference) at week 24 compared to baseline.

Aim 2. Assess changes in he profile inflammatory and of immunoactivation :

- Aim 2a. Assess the changes in the activation immune of the T cell compartment at week 24 compared to baseline.
- Objective 2b. Percentage of patients with reduced inflammatory and bacterial translocation markers at week 24 compared to baseline.

Objective 3. To evaluate changes in arterial stiffness levels measured by pulse wave velocity at week 24 compared to baseline.

Aim 4. Proportion of Participants with decline of >20% of TMAO in the week 24 compared to baseline.

Aim 5. Proportion of Participants with increase of >2 points in the scale MEDAS adherence to the Mediterranean diet at week 24 compared to baseline

Objective 6. Proportion of participants who improve in the quality of life questionnaire. EQ-5D life at week 24.

Objective 7. Evaluate the persistence of all changes included in objectives 1 to 6 at week 48 (24 weeks after the end of the intervention)

Objective 8. To assess the burden of subclinical atherosclerotic coronary disease and changes 1 year after intervention.

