5.3. Definition of the variables of study

Main Variables

- Total cholesterol, cLDL , cHDL , triglycerides in mg/ dL . It will be measured at baseline, week 24 and 48.

Secondary Variables

- Number, size and composition of lipoprotein particles by proton magnetic resonance spectroscopy at baseline, week 24 and 48.
- Anthropometric profile (weight, body mass index, abdominal circumference) at baseline, week 24 and 48.
- CD 3,CD 45,CD4,CD8,CCR7,CXCR3,CCR6,CD103,FOXP3,CD25,CD45RA and CD45RO. Quantification in blood in visits basal, 24 weeks and 48 weeks of cells with markers.
- IL-6, TNF-alpha, IFN-gamma, sCD163, sCD14, MADCAM-1, sCD14 and LPS. Quantification in serum in visit basal, 24 weeks and 48 weeks of
- Rigidity arterial extent by the speed of vole of pulse in the visit basal, week 24 and 48.
- Levels of Trimethylamine -N-Oxide serum (TMAO) in the in the visit basal, week 24 and 48.

- Scale MEDAS of adherence to the diet Mediterranean measures in the Baseline visit, week 24 and 48
- Questionnaire of quality of life EQ-5D in the visit basal, week 24 and 48.
- Presence of atheromatous plaque at the coronary level at the baseline visit and at week 48
- Presence of calcium, fibrous and fatty fraction in the coronary plaque at the baseline visit and at week 48
-

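### Coronary CT outcomes come from routine reading in an open trial, and nothing keeps the readers from knowing the arm (secondary Objective 8; cheap improvement, low priority)

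*Protocol*

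**What the plan says.** The Summary of the protocol gives the design as "Rehearsal clinical randomized open", that is, an open randomized trial, with a single participating hospital. Coronary CT was added in version 1.2. Section 2 (History of versions) justifies it with "Given the possibility of having CCTA experience for coronary plaque detection at our center", so the scans are done in-house.

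Objective 8 in Section 4 reads "To assess the burden of subclinical atherosclerotic coronary disease and changes 1 year after intervention". Section 5.3 lists two CT outcomes among the secondary variables: "Presence of atheromatous plaque at the coronary level at the baseline visit and at week 48" and "Presence of calcium, fibrous and fatty fraction in the coronary plaque at the baseline visit and at week 48". The variable list in the Summary adds the number of plaques, composition as percentages of fibrous tissue, calcium and fat, and the coronary calcium index.

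Task 7 in Section 6 settles how the scans are made and read: "CCTAs in the study will be performed in an identical manner to those performed daily in our center as part of routine clinical practice", and then "using identical protocols for both image capture and interpretation/reporting". No section describes a reading masked to arm.

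**The concern.** Task 7 does more than stay silent. It makes the routine interpretation and reporting process the source of study outcomes. A routine process is set up for care. As described here, it includes no step that separates the reader from the allocation.

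Counting plaques and assigning their composition call for judgement, and the protocol gives no scoring method that would limit it. A reader who knows that a participant received the personalized diet may, without intending to, read the scan more favourably. That would bias the comparison between arms for Objective 8, the objective that the CT amendment was written to serve. Each participant has two contrast CT scans for it, so the result deserves simple protection.

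**Working it through.** No arithmetic settles this point. The protocol states no effect size, standard deviation, power or test for the CT outcomes, so there is no figure to reproduce. The check is to set the relevant parts side by side.

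1. **Is allocation concealed from anyone?** No. The Summary gives the design as open.

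2. **Is CT reading separated from the site?** No. There is one hospital, and Task 7 uses its daily CT practice. No central or independent reading is described.

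3. **When could the arm be known?** Possibly at both scans. Section 6 places randomization at the initial visit, before the Visit 1 (baseline) measurements. Section 7, stage 2, places it at the selection visit. The study calendar places it at the same visit as the first CT. On each of these accounts the arm may already be assigned when the baseline scan is read, and it is certainly assigned at week 48. The baseline reading therefore cannot be assumed to be free of the same influence.

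4. **Which outcomes are exposed?** Plaque number and composition most, because they rest on judgement. Plaque presence also needs a reading. The calcium index is likely to depend less on the reader.

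5. **Do protections elsewhere in the protocol reach the scans?** No.
   - Lipoprotein NMR (Task 2b) and TMAO (Task 6) are measured on stored samples at outside laboratories after follow-up.
   - Section 9 pseudo-anonymizes the samples.
   - Section 10 limits the database to a study ID.
   - None of these provisions is applied to CT images or CT requests before reading.

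6. **What is not affected?** The main variables in Section 5.3 are total cholesterol, LDL, HDL and triglycerides, which are laboratory measurements.

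Steps 1 to 5 show that nothing in the protocol prevents a reader from knowing the arm. They do not show that any reader will know it.

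**The case against.** The strongest reply is that Task 7 only standardizes technique. Using the same protocols as daily practice does not tell anyone the arm, and a routine reader has no evident need to know a dietary allocation. The research team listed on the first pages belongs to the HIV and Endocrinology services. The nutritionist and Endocrinology carry out the dietary work. Task 7 mentions cardiologists only for directing the preparation of participants. No section gives them a part in randomization, counselling or follow-up visits.

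Much of this stands. It makes knowledge of the arm less likely, and it is why the point is a risk and not an error. But separation by habit is not a rule. The protocol does not say what a CT request or its clinical information may contain.

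Three stronger readings are tempting, and the documents support none of them:

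- A reader might infer that the CT readers are told the arm. No section says so.
- A reader might infer that access to the baseline report when the week-48 scan is read biases the trial. The protocol does not say that the earlier report is shown. If it were, it would be available in both arms alike. Without knowledge of the arm it may affect the size of the measured change, but it does not favour either arm.
- A reader might want to express the risk as an inflated false-positive rate based on the 67 and 33 participants. That would need an invented reading shift and a continuous outcome measured in all 100. Plaque presence is binary and plaque number is a count. Composition exists only in participants who have plaque, and how many will have it is not stated. Objective 8 also names no between-arm test.

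**Conclusion.** The point holds as an unprotected risk. CT outcomes come from routine interpretation in an open single-centre trial, and no provision keeps the arm from the readers. The consequence would be reading bias between arms in Objective 8, mainly in plaque number and composition.

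Its size cannot be derived from the document, and no figure is offered. The conclusion rests on two assumptions: that the CT outcomes will be compared between the randomized arms, which the comparative design implies although Objective 8 does not spell it out, and that plaque counting and composition leave room for judgement.

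The CT measures are secondary, and the lipid results do not depend on them. This is a cheap improvement of low priority.

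**What to change.** Add two statements to Task 7 in Section 6:

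- CT requests, and any clinical information passed to the readers, do not state the study arm.
- The existing cardiac-imaging readers record the study measures (plaque presence and number, composition, calcium index) for the baseline and week-48 scans without knowledge of the arm.

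The other scan's report need not be withheld. Apart from the arm not being stated, the clinical report for care stays as it is.

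The cost is minor handling of request forms and a separate record of the study measures. No extra reader and no extra scan are needed.

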7. PERIOD OF THE STUDY

For can carry to cape all he project it we have divided in different stages:

1. Preparation and validation of the protocol. Patient preselection circuits and diagnostic tests.

January 2025 to February 2025.

This phase will be carried out by the researchers: Design of the patient selection circuit within the HIV unit and promotion of the study among the professionals of the unit focused on the need to address the optimization of the lipid profile of this group of people. We will review the processing of the samples (labeling of the samples, contact with the BioBank service , presentation of the study to the doctors for their knowledge). An anonymous registry of candidate patients will be created.

2. Recruitment of patients

From March 2025 to March 2026. It is estimated that it will take at least one year to recruit the 100 patients.

Recruitment will be carried out at the Infectious Diseases Service of Hospital del Mar (HM). The referent will be [name] [name] (IP). The researchers who will coordinate the recruitment process will be [name]. Patients who meet the inclusion criteria will be referred to a specific consultation created ad hoc to carry out the selection visit. This phase will be carried out interchangeably by [name], [name], [name], [name] or [name] [name]. During this visit, informed consent will be signed, the first sample will be extracted for the complete analysis and general data will be collected: background, history of HIV infection, treatment history and the questionnaires and the participant will be randomized.

3. Follow-up of the patient during 48 weeks. From March 2025 to October 2026.
At this stage, the specific intervention itself will be carried out. Nutritionist researcher [name] together with [name] and [name] [name] from the Endocrinology service will carry out a complete nutritional assessment. Anthropometric measurements and a measurement of the speed of movement will be carried out. of the vibe of pulse. HE will perform follow-up according to it notarized.
4. study visits (March 2025 to October 2026). The final study visit with follow-up at 48 weeks will be carried out in all participants. The tests contemplated in the protocol will be carried out. This stage will be carried out by the equipment of the [name] ([name] together with the [name] and [name] [name]).
5. Sample collection and processing: blood collection and processing to obtain PBMCs , plasma and serum. The processing and conservation of the samples will be carried out in the IMIM laboratory by [name] -[name] and [name].
6. Sample preparation for FACS . Once initial recruitment is complete, preserved samples will be thawed, stained and prepared for FACS ([name], Dra [name]). Data reading and interpretation will be performed by [name] and an external collaborator ([name] (University of California).
7. Sample preparation and shipment to Metabolomics Platform IISPV, CIBERDEM . Rovira i Virgili University , Bisofer Teslab . When the follow-up is completed, samples will be sent (baseline samples , 24 weeks and 48 weeks). weeks) to the Rovira i Virgili University for further processing and interpretation of the results of the lipoprotein subclasses.
8. Preparation and shipment of plasma samples to Middlesex University , London (Dr. laboratory [name]). Once follow-up is complete, samples (baseline, 24-week and 48-week samples) will be sent to the Middlesex Hospital. university for the determination of TMAO according to the described protocol.
9. Analysis and publication of results (from January 2026 (preliminary) to December 2026) will be carried out by the entire research team.

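### The calendar in Section 7 cannot hold 48 weeks of follow-up: the last week-48 visit falls in January to March 2027, after the stated ends of follow-up (October 2026) and study (December 2026)

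*Protocol*

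**What the plan says.** **Dates.** Section 7 of the protocol gives a staged calendar:

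- Stage 2, recruitment: "From March 2025 to March 2026. It is estimated that it will take at least one year to recruit the 100 patients".
- Stage 3: "Follow-up of the patient during 48 weeks. From March 2025 to October 2026".
- Stage 4, also dated March 2025 to October 2026: "The final study visit with follow-up at 48 weeks will be carried out in all participants".
- Stage 8, TMAO: "Once follow-up is complete, samples (baseline, 24-week and 48-week samples) will be sent". Stage 7 sets the same condition for the lipoprotein samples, and Section 6, Task 2b, says that "when recruitment and monitoring have been completed, the analysis of the lipoprotein subclass profile will be performed".
- Stage 9: "Analysis and publication of results (from January 2026 (preliminary) to December 2026".

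The Summary gives the overall duration as "January 2025- December 2026" and enters 48 weeks under "Duration of the study for the patient". Board 1 allows the week-48 visit from 7 days early to 14 days late.

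**Pulse wave velocity.** Board 1 marks it at baseline and week 24 only. Section 5.3 lists it at baseline, week 24 and week 48. Objective 7 asks whether the changes in Objectives 1 to 6 persist at week 48, and arterial stiffness is Objective 3.

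**The concern.** Recruitment that closes in March 2026, a full 48 weeks for everyone, and follow-up that ends in October 2026 exclude one another. March to October 2026 is about seven months; 48 weeks is about eleven. The December 2026 study end does not rescue it.

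The protocol does not say which date yields. If the 48 weeks prevail, the week-48 data (Objective 7), the follow-up coronary CT (Objective 8) and the NMR and TMAO results (Objectives 1b and 4, including their week-24 values, because the assays wait for the end of follow-up) all arrive after the stated end of study and analysis. If the calendar prevailed, late recruits would lose their week-48 data.

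The pulse wave velocity gap is a different defect with a smaller consequence: staff who work from Board 1 would skip a planned week-48 measurement.

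**Working it through.** **Inputs.** Recruitment March 2025 to March 2026; follow-up to October 2026 (Section 7, stages 2 to 4). Study end December 2026 and 48 weeks per patient (Summary). Week-48 window −7/+14 days and week-24 window ±7 days (Board 1). 48 weeks = 336 days; with the window, 329 to 350 days. 24 weeks = 168 days.

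**1. Can the stated end be reproduced?** Last week-48 visit = last randomisation + 336 days.

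| Last randomisation | −7 days | Nominal | +14 days |
|---|---|---|---|
| 28 Feb 2026 (exactly one year) | 23 Jan 2027 | 30 Jan 2027 | 13 Feb 2027 |
| 1 Mar 2026 | 24 Jan 2027 | 31 Jan 2027 | 14 Feb 2027 |
| 31 Mar 2026 | 23 Feb 2027 | 2 Mar 2027 | 16 Mar 2027 |

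None falls in October or December 2026. If the March 2026 close is read as the last screening, Board 1 allows up to 28 more days before baseline (28 April 2026). The last visit is then 30 March 2027, or 13 April with +14 days.

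**2. Working back.** Latest randomisation = end date − 336 days (−329 with the early window).

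| End date | Nominal | Early window | Recruitment days from 1 Mar 2025 (nominal, inclusive) |
|---|---|---|---|
| 31 Oct 2026 | 29 Nov 2025 | 6 Dec 2025 | 274 |
| 31 Dec 2026 | 29 Jan 2026 | 5 Feb 2026 | 335 |

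Both are short of the one year that the protocol calls a minimum. This step needs no accrual assumption.

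**3. How many participants?** The protocol gives no accrual pattern. Assume uniform accrual from 1 March 2025 to 31 March 2026, which is 396 days inclusive:

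- past 31 October 2026: 1 − 274/396 = 30.8%, about 31 of 100;
- past 31 December 2026: 1 − 335/396 = 15.4%, about 15 of 100.

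Taking each stated month at its first or last day, with or without the 7-day early window, gives 23 to 42 of 100 (October) and 7 to 25 of 100 (December). Allowing the 28-day screening lag as well raises the upper ends to 49 and 33.

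**4. What does fit?** Last week-24 visit: 31 March 2026 + 168 days = 15 September 2026, or 22 September with +7 days. Week-24 visits and the routine lipids that are the main variables lie inside the stated follow-up.

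**5. Size of the overrun.** From 31 October 2026 to 2 March 2027 is 122 days, and to 16 March 136 days. From 31 December 2026 the figures are 61 and 75 days.

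**6. Pulse wave velocity.** No arithmetic applies. Section 5.3 and Objective 7 (through Objective 3) plan it at week 48. Section 6 places it at the baseline visit and has both arms repeat the baseline assessments at week 48. Board 1 leaves the week-48 cell empty. The coronary CT row just below keeps its week-48 mark, so a lost column in the text extraction is unlikely.

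**The case against.** The best defence is that Section 7 is a project timetable and the recruitment line is expressly an estimate. No rule cuts anyone's follow-up short, the week-48 visit is stated for all participants, and the week-24 main variables are unaffected. On the natural reading the trial simply runs late and no data are lost. That is right as far as it goes, and it limits the severity. It does not make the dates correct: they are still the protocol's only statement of when follow-up, study and analysis end, and two assays are tied to the end of follow-up.

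The participant counts depend on an assumed accrual pattern and matter only if the calendar were enforced. The figures of 31 and 15 use the latest recruitment close, 31 March 2026. The upper ends of 49 and 33 need a screening lag that Section 7 does not suggest, since it randomises at the selection visit, although Board 1 places randomisation at baseline. The date conflict needs none of these assumptions.

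On pulse wave velocity, the Section 6 wording is weak support. It asks for all baseline procedures at both week 24 and week 48, yet Board 1 schedules no coronary CT at week 24, so it cannot be meant literally. Section 5.3 and Objective 7 carry the point.

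The analysis from January 2026 is labelled preliminary and is not an error.

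**Conclusion.** The concern holds and should be fixed. On the protocol's own figures the last week-48 visit falls between 31 January and 2 March 2027 for a last randomisation in March 2026. That is roughly three to four months after the stated end of follow-up and one to two months after the stated end of study. No reading of the months, the visit window or the screening lag removes the conflict.

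The effect is on Objectives 7 and 8 and on the NMR and TMAO results. Routine week-24 lipids are safe. The counts of about 31 and 15 participants rest on uniform accrual and would be losses only if the calendar dates overrode the 48 weeks, which nothing in the protocol says.

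The missing week-48 mark for pulse wave velocity is a separate, minor inconsistency.

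**What to change.** **Dates.** Reconcile the overall duration in the Summary with Section 7, stages 2, 3, 4 and 9, by one of two routes:

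- Keep recruitment to March 2026 and 48 weeks for all. Restate the end of follow-up as March 2027 or later: 16 March with the late window, 13 April if March 2026 means the last screening. Set a later end of study and analysis that leaves time for the assays.
- Keep the end dates. State the recruitment close they imply (29 November 2025 for 31 October 2026, or 29 January 2026 for 31 December 2026; each 7 days later if the early window is used) and the sample size expected by then. Assay time would have to come off these dates as well.

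The first route costs text changes and moves the end of follow-up by 122 to 136 days without a screening lag. The study end moves at least 61 to 75 days past 31 December 2026, plus assay and analysis time that the protocol does not state. The second route costs participants.

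**Pulse wave velocity.** Reconcile Board 1 with Section 5.3 and Objective 7. If the week-48 measurement is intended, as both say, mark the cell. This adds one measurement at a visit already held in person.
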